## **6.2 Efficacy Analysis Methods**

Continuous variables will be tabulated by Cohort and presented with summary statistics (i.e., median and range). Categorical variables will be summarized by Cohort in frequency tables by means of counts and percentages.

### **6.2.1 Primary Endpoint**

Exact binomial estimates with 95% confidence intervals (CIs) will be calculated for the analysis of the main endpoint (ORR according to RECIST v1.1 criteria).

### **6.2.2 Secondary Endpoints**

Time-to-event endpoints (DR, PFS and OS) and their set time estimates (i.e. PFS3, PFS6 and 1y-OS) will be analyzed according to the Kaplan-Meier method.

A log-rank test or Cox regression for time-to-event endpoints could be performed as supportive analysis to compare both Cohorts.

If relevant, efficacy parameters versus baseline covariates will be analyzed and appropriate test will be used (i.e., the Fisher exact test and logistic regression for categorical variables, the log-rank test or Cox regression for time-to-event variables, etc.).

If appropriate, exploratory multivariate models (main effects or including interaction terms, if appropriate) will include all prognostic factors/covariates widely reported and recognized by oncologists: Cohort (BRCA (+) vs. BRCA (-) or unknown), BRCA (1 vs. 2 in cohorts A and A1), initial dose (7 mg FD vs 3.5 mg/m^2), age, age at diagnosis, race (Caucasian vs. other), baseline Eastern Cooperative Oncology Group performance status (ECOG PS) (0 vs. >0), histology type (Ductal vs. lobular carcinoma), histology grade (poorly vs. other), stage at diagnosis, primary tumor site (unilateral breast vs. bilateral), hormone receptor positive (estrogen or progesterone receptor +, or both +) vs. triple negative, HER-2 receptor (positive vs. negative), site of current disease such as liver metastases (yes vs. no), CNS metastases (yes vs. no), lung metastases (yes vs. no), non-visceral (including bone, skin, subcutaneous and lymph node vs. other), number of prior metastatic sites (1 vs. >1), body mass index (BMI), height, weight, body surface area (BSA), time from diagnosis to first infusion, prior surgery (yes vs. no), prior radiotherapy (yes vs. no), prior advanced treatment lines, prior advanced chemotherapy lines (0-1 vs. 2-3), prior anthracyclines (yes vs. no), prior taxane (yes vs. no), prior platinum (yes vs. no), prior PARPi (yes vs. no), last prior therapy PFS, first advanced chemotherapy PFS, last advanced chemotherapy PFS, PFS for anthracycline, taxane and platinum therapy, hormonotherapy (yes vs no), adjuvant/neoadjuvant therapy (yes vs no), platinum-free interval (in months), presence of any bulky (< 50 mm vs.  $\geq$  50 mm) lesion, albumin at baseline, CA-15.3 or 27.29 at baseline, any relevant concomitant medication at baseline (to be determinate by the oncologist) (yes vs. no) and the sum of all target lesion diameters.

All variables with a good percentage of valid cases (approximately  $\geq$  90%) and with a p-value lower than 0.10 in the univariate analysis will be included in the exploratory multivariate analysis. Within the multivariate stepwise Logistic/Cox regression analysis, the chosen significance level for entering an explanatory variable into the model will be 0.05 (for all variables not in the model, the one with the smallest p-value is entered if the p-value is less than or equal to the specified significance level). The significance level for removing an explanatory variable from the model is 0.05 (for all variables in the model, the one with the largest p-value will be removed if the p-value exceeds the specified significance level). The parameter estimates, hazard ratios and p-values for hazard ratios of the variables retained in the model will be presented.

If appropriate, multivariate analysis will be produced for a relevant subgroup of patients (e.g. by cohort).

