3.2. SECONDARY

- To further characterize the antitumor activity of PM01183 in terms of duration of response (DR), clinical benefit [ORR or stable disease lasting over three months (SD > 3 months)], PFS, and one-year overall survival (1y-OS).
- To evaluate whether the presence of a known germline mutation in BRCA 1/2 predicts response to PM01183 in MBC patients.
- To explore the activity of PM01183 in specific breast cancer subpopulations according to hormonal receptor status, HER-2 overexpression, number and/or type of prior therapies, or according to other available histological/molecular classifications/parameters.
- To evaluate the safety profile of this PM01183 administration schedule (Day 1, q3wk) in this patient population.
- To analyze the pharmacokinetics (PK) of PM01183 in this patient population.
- To explore PK/PD (pharmacokinetic / pharmacodynamic) correlations, if applicable.
- To evaluate the pharmacogenomic (PGx) expression profile of selected putative markers potentially predictive of response to PM01183, in tissues from tumor samples.

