8.3.1. Efficacy Analyses

For the primary endpoint (ORR) the exact binomial estimator and its 95% CI will be used.

The time-to-event variables (DR, PFS and OS) and their set time estimates (e.g., PFS3, PFS6 and 1y-OS) will be analyzed according to the Kaplan-Meier method.

Exploratory comparison of the efficacy results between the two study cohorts will be performed by means of Fisher analysis and logistic regression (ORR), and of log-rank test/Cox regression (time-to-event variables). Additionally, if clinically appropriate, the two cohorts might be pooled into one, whenever differences between cohorts are considered not relevant. In such case, the point estimates and their 95% CIs will be also reassessed in order to obtain more accurate calculations.

Exploratory subgroup analyses (e.g., triple negative, hormonal receptor status, HER-2 overexpression, etc.) will be also performed depending on the sample sizes of each subgroup, if appropriate.

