#### ***3.2 Secondary Objectives***

- To further characterize the antitumor activity of PM01183 in terms of duration of response (DR), clinical benefit [ORR or stable disease lasting over three months (SD  $> 3$  months)], PFS, and one-year overall survival (1y-OS).
- To evaluate whether the presence of a known germline mutation in BRCA1/2 predicts response to PM01183 in MBC patients.
- To explore the activity of PM01183 in specific breast cancer subpopulations according to hormonal receptor status, HER-2 overexpression, number and/or type of prior therapies, or according to other available histological/molecular classifications.
- To evaluate the safety profile of this PM01183 administration schedule (Day 1, q3wk) in this patient population.
- To analyze the pharmacokinetics (PK) of PM01183 in this patient population.
- To explore PK/PD (pharmacokinetic / pharmacodynamic) correlations, if applicable.
- To evaluate the pharmacogenomic (PGx) expression profile of selected putative markers potentially predictive of response to PM01183, in tissues from archived tumor samples.

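### The only adjusted estimate of the BRCA effect is shown only if it survives p-value selection; one pre-specified model with the cohort term forced in would cure this

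*SAP*

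**What the plan says.** **Objective.** Protocol 3.2 lists, among the secondary objectives, "To evaluate whether the presence of a known germline mutation in BRCA 1/2 predicts response to PM01183 in MBC patients". SAP 3.2 repeats it, and Protocol 1.3 describes the question as a goal of the trial. Protocol 6.5 and 8.2.1 state that randomisation does not apply.

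**Unadjusted comparison.** Protocol 8.3.1: "Exploratory comparison of the efficacy results between the two study cohorts will be performed by means of Fisher analysis and logistic regression", with log-rank and Cox methods for the time-to-event endpoints. SAP 11.3.3 adds univariate tables for response, PFS and OS covering every covariate in the 6.2.2 list, with no p-value filter.

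**Adjusted model.** SAP 6.2.2 says that exploratory multivariate models, if appropriate, "will include all prognostic factors/covariates widely reported and recognized by oncologists". The list opens with "Cohort (BRCA (+) vs. BRCA (-) or unknown), BRCA (1 vs. 2 in cohorts A and A1" and runs to 45 items (43 if prior PFS on anthracycline, taxane and platinum counts as one). The next paragraph narrows it. Variables need about 90% valid cases, and only those "with a p-value lower than 0.10 in the univariate analysis will be included in the exploratory multivariate analysis". Then "the chosen significance level for entering an explanatory variable into the model will be 0.05" and "The significance level for removing an explanatory variable from the model is 0.05". Estimates are to be presented for the variables that remain. The shells for Tables 11.3.3.2, 11.3.3.4 and 11.3.3.6 repeat the screen with no exception for cohort.

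**Starting dose by cohort.** The safety groups in SAP 12.2.1 and 12.4 show Cohort B only at 7 mg FD, Cohort A at both starting doses, and Cohort A1 only at 3.5 mg/m².

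**The concern.** Cohorts A and B can differ in prior lines, platinum exposure, receptor status and starting dose. A raw contrast cannot separate BRCA status from these factors, so an adjusted estimate is the natural companion to the planned unadjusted one. The SAP's only route to an adjusted estimate makes its appearance depend on its own p-value.

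Two things follow. In many data sets there will be no adjusted BRCA estimate at all. Where there is one, it has been selected for being far from the null, so on average it overstates a moderate effect. Confounders are handled the same way: a factor strongly tied to cohort but only moderately tied to response can be left out because its p-value missed a threshold.

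A reader of the study report who sees an adjusted odds ratio for BRCA would not know that it was printed because it was significant.

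**Working it through.** **1. Anchors from the plan.** The documents give no power for the BRCA comparison, so the cohort designs (Protocol 8.2, SAP 5.1) supply the rates and sizes. Their rejection counts reproduce with the stated null-variance test:
- Cohort A: (17/53 − 0.20)/√(0.20×0.80/53) = 2.20, while 16 responders give 1.85. So 17 is the critical count.
- Cohort B: (12/64 − 0.10)/√(0.10×0.90/64) = 2.33, while 11 give 1.92. So 12 is the critical count.

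Inputs taken forward: 53 patients at 40% and 64 at 25%, the rates that Protocol 1.3 calls worthy of further research. True odds ratio: (0.40/0.60)/(0.25/0.75) = 2.00.

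**2. Cohort as the only candidate.** This isolates the effect of the thresholds from any noise covariates. With a responders in A and b in B:
- log OR = ln[a(64−b)/((53−a)b)]
- SE = √[1/a + 1/(53−a) + 1/b + 1/(64−b)]
- retained if the two-sided p is at most 0.05, which also meets the 0.10 screen.

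Hand check at expected counts (21.2, 31.8, 16, 48): SE = 0.402, and ln 2/0.402 = 1.72. P(Z > 1.96 − 1.72) is about 0.41.

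Exact enumeration over both binomials (mean OR is the exponential of the mean log OR among retained trials):

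| True rates | n | Retained | Mean OR if retained | True OR | Inflation of log OR |
|---|---|---|---|---|---|
| 40% v 25% | 53 v 64 | 40% | 3.02 | 2.00 | 1.6-fold |
| 40% v 25% | 73 v 37 | 33% | 3.46 | 2.00 | 1.8-fold |
| 40% v 10% | 53 v 64 | 97% | 6.6 | 6.00 | 1.06-fold |

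The second row is an assumption. It takes the expected total of about 110, Cohorts A and A1 full and coded together as BRCA(+) (53 + 20 = 73), and 110 − 73 = 37 in Cohort B.

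The smallest odds ratio above 1 that can be retained with 53 v 64 comes from 33/53 v 28/64: (33×36)/(20×28) = 2.12. That already exceeds 2.00. At the design rates, every favourable estimate that the rule can print from cohort alone is too high.

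**3. Full rule.** The simulation used cohort plus 44 covariates, a screen at 0.10 and stepwise selection at 0.05/0.05. Two covariates were truly prognostic (log OR 0.6 each), the common correlation was 0.3, and none was associated with cohort.

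| True rates | n | Runs | Retained | Mean OR if retained | Mean OR, forced short model |
|---|---|---|---|---|---|
| 40% v 25% | 53 v 64 | 300 | 29% | 3.7 | 2.07 |
| 40% v 25% | 73 v 37 | 300 | 25% | 4.3 | 2.08 |
| 40% v 10% | 53 v 64 | 200 | 94.5% | 8.2 | 6.9 |

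The Monte Carlo standard error of the 29% is √(0.29×0.71/300) = 2.6 points. The forced model held cohort and the two true factors and was reported in every run.

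**4. Information available.** Expected responders: 53×0.40 + 64×0.25 = 37.2, fewer than one per candidate for 45 candidates. If the other 44 were null and independent, 44×0.10 = 4.4 would pass the screen by chance.

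**The case against.** The best defence is that the SAP never ties the stepwise model to the BRCA objective. It calls the model exploratory and conditional. The cohort comparison is planned elsewhere without selection: Fisher and logistic regression, unfiltered univariate odds and hazard ratios, and exact ORR intervals by cohort. This stands. A reader might infer that the BRCA objective has no estimate unless it is significant; the documents do not support that. What is missing is an unselected *adjusted* estimate.

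It also stands that most of the non-retention is low power. Two-sided power for 40% v 25% is 41% at the 0.05 level, so a forced model would usually be non-significant too. Its advantage is that the estimate and interval are shown without selection.

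Three stronger readings should be resisted.
- A reader might infer that any reported BRCA effect is inflated. That depends on power; at 40% v 10% the cohort-only inflation is 1.06-fold.
- A reader might infer that the 90%-valid rule damages the BRCA question by dropping BRCA1 v 2 and platinum-free interval. SAP 6.2.2 limits BRCA1 v 2 to Cohorts A and A1 and allows models by cohort, and prior platinum (yes/no) remains a candidate. The BRCA(+) v unselected contrast is not harmed.
- A reader might infer that a futility stop of Cohort B at 30 makes matters much worse at these same rates. That stop needs fewer than three responses, which has probability 1.1% when the true rate is 25%.

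**Conclusion.** The point holds for the adjusted estimate only. As written, the SAP presents an adjusted BRCA effect only after selection on its own p-value, and it leaves confounder control in non-randomised cohorts to the same rule. It is a recommended improvement to an exploratory analysis and does not touch the primary endpoint.

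Size for ORR at the design rates: retained in about 40% of trials with a mean odds ratio of about 3.0 against a true 2.0. This needs only the documents' rates, sizes and thresholds, with cohort as the sole candidate. The full-rule figures (about 29% and 3.7) depend on the assumed correlation and prognostic effects, and on all 45 candidates being available; the 90%-valid filter would probably remove some. The simulation had no confounding with cohort, so it does not measure the bias from dropping a confounder. PFS and OS were not computed; the same rule applies to them.

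**What to change.** Add to SAP 6.2.2 one pre-specified model each for ORR (logistic), PFS and OS (Cox) in Cohorts A and B, with A1 excluded. Force in cohort plus a short set already on the covariate list: number of prior chemotherapy lines, triple-negative yes/no, prior platinum yes/no and ECOG PS. Add prior PARPi if any Cohort A patient had it; SAP 8.9 plans that split within Cohort A. Report the cohort estimate and its 95% CI whatever the p-value.

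The safety groups list Cohort B at one starting dose only, so dose cannot be cleanly adjusted for across the two cohorts. Handle it by a sensitivity analysis restricted to patients who started at 7 mg FD.

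Keep the stepwise model, labelled hypothesis-generating, and reconcile the sentence saying that models include all listed covariates with the selection rule that follows it.

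Cost: SAP wording, one extra model per endpoint and the dose sensitivity run, with no new data. The estimate may be non-significant with a wide interval. With about 37 expected responders and five or six terms (37.2/6 = 6.2 per term), the set should not grow.

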### 11.3.3 Exploratory Univariate and Multivariate Analyses

Table 11.3.3.1 Univariate analysis of response rate

Variable label	Variable values	DF	Estimate	Standard error	Wald chi-square	Pr > ChiSq	Odds ratio estimate	95% Odds Ratio confidence limits

(See list of covariates in section 6.2.2).

Table 11.3.3.2 Multivariate analysis of response rate

Analysis of Maximum Likelihood Estimates								
Variable label	Variable values	DF	Estimate	Standard error	Wald chi-square	Pr > ChiSq	Odds ratio estimate	95% Odds Ratio confidence limits

(See list of covariates in section 6.2.2. Only those covariates with a p-value < 0.10 in univariate analysis and with a 90% of valid observations will be included).

Table 11.3.3.3 Univariate analysis of PFS

Variable label	Variable values	DF	Parameter estimate	Standard error	Chi-square	Pr > ChiSq	Hazard ratio	95% Hazard ratio confidence limits

(See list of covariates in section 6.2.2).

Table 11.3.3.4 Multivariate analysis of PFS

Analysis of Maximum Likelihood Estimates								
Variable label	Variable values	DF	Parameter estimate	Standard error	Chi-square	Pr > ChiSq	Hazard ratio	95% Hazard ratio confidence limits

(See list of covariates in section 6.2.2. Only those covariates with a p-value < 0.10 in univariate analysis and with a 90% of valid observations will be included).

Table 11.3.3.5 Univariate analysis of OS

Variable label	Variable values	DF	Parameter estimate	Standard error	Chi-square	Pr > ChiSq	Hazard ratio	95% Hazard ratio confidence limits

(See list of covariates in section 6.2.2).

Table 11.3.3.6 Multivariate analysis of OS

Analysis of Maximum Likelihood Estimates								
Variable label	Variable values	DF	Parameter estimate	Standard error	Chi-square	Pr > ChiSq	Hazard ratio	95% Hazard ratio confidence limits

(See list of covariates in section 6.2.2. Only those covariates with a p-value < 0.10 in univariate analysis and with a 90% of valid observations will be included).

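### Read from the SAP's own Wald table, the p<0.10 screen for the response model drops any categorical covariate with a level in which no patient, or every patient, responds

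*SAP*

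**What the plan says.** SAP 6.2.2 lists the candidate covariates, many of them yes/no. It keeps those with about 90% valid values and "with a p-value lower than 0.10 in the univariate analysis will be included in the exploratory multivariate analysis". The footnote to each multivariate table in SAP 11.3.3 repeats the rule: "Only those covariates with a p-value < 0.10 in univariate analysis and with a 90% of valid observations will be included". Neither place names the test behind that p-value.

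For response, one output is labelled univariate: "Table 11.3.3.1 Univariate analysis of response rate". Its columns are an estimate, a standard error, a "Wald chi-square", the resulting p-value and the odds ratio with limits. No other test appears in it.

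Earlier in 6.2.2, for efficacy against baseline covariates and only if relevant, the SAP mentions "the Fisher exact test and logistic regression for categorical variables". That sentence is not linked to the 0.10 screen.

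After the screen comes stepwise selection: "the chosen significance level for entering an explanatory variable into the model will be 0.05". For removal, "the one with the largest p-value will be removed if the p-value exceeds the specified significance level", again at 0.05. No test is named for entry or removal. Models by cohort are allowed. Neither document gives a rule for a covariate level with no responders or only responders.

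**The concern.** A programmer who follows the shell will read the screening p-value from the Wald column. That statistic fails when a level has no responders or only responders. The estimated log odds ratio runs off without limit, its standard error grows faster, and the p-value goes to about 1. The covariate is then excluded from the adjusted model although the data may show a very clear difference, while a covariate with a weaker association is kept.

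Both documents make it a secondary objective to explore activity in specific subpopulations. A sizeable level with no responses is a finding this exploration should pick up. As the shell stands, it would be listed with a p-value near 1 and an unusable odds ratio, and then left out of the model.

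**Working it through.** **Inputs.** The SAP states no figure for the screen, so I took responder totals from its design section (SAP 5.1): 17 of 53 in Cohort A and 12 of 64 in Cohort B, the counts that reject the null hypothesis. They follow from the stated null-variance test: 53×0.20 + 1.96×√(53×0.20×0.80) = 16.3, so 17; and 64×0.10 + 1.96×√(64×0.10×0.90) = 11.1, so 12. Level sizes and response rates within levels are assumptions; the documents give none.

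**Formulas.** For a/n₁ responders in one level and c/n₂ in the other:

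- Wald: b = ln[a/(n₁−a)] − ln[c/(n₂−c)]; SE² = 1/a + 1/(n₁−a) + 1/c + 1/(n₂−c); compare (b/SE)² with chi-square on 1 df.
- Likelihood ratio: G = 2(L₁ − L₀), where L₁ is the binomial log-likelihood with separate rates and L₀ with a common rate.

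**One responder in the level (1/20 vs 16/33).** b = ln(1/19) − ln(16/17) = −2.884. SE = √(1 + 1/19 + 1/16 + 1/17) = 1.083. (b/SE)² = 7.08, p = 0.008, so it passes.

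**No responder (0/20 vs 17/33).** The 1/a term has no finite value and the fit never settles. Hold the other level at ln(17/16) and let π be the fitted response rate in the empty level. Then SE² = 1/[20π(1−π)] + 1/17 + 1/16. At b = −10 the SE is 32 (p = 0.76); at b = −15 it is 392 (p = 0.97). A Newton-Raphson fit with a gradient criterion of 1e-8 stops at b = −19.3, SE = 3306, p = 0.995. The likelihood ratio is well behaved: L₀ = 17 ln(17/53) + 36 ln(36/53) = −33.25; L₁ = 17 ln(17/33) + 16 ln(16/33) = −22.86; G = 20.8, p < 0.0001.

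**Other splits.**

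| Split | Wald p | Likelihood-ratio p | Fisher p | Wald screen |
|---|---|---|---|---|
| 0/20 vs 17/33 | 0.995 | <0.0001 | <0.0001 | out |
| 1/20 vs 16/33 | 0.008 | 0.0003 | 0.0009 | in |
| 2/20 vs 15/33 | 0.014 | 0.005 | 0.014 | in |
| 3/20 vs 14/33 | 0.047 | 0.032 | 0.067 | in |
| 0/10 vs 17/43 | 0.995 | 0.003 | 0.021 | out |
| 0/7 vs 17/46 | 0.99 | 0.015 | 0.082 | out |
| 0/3 vs 17/50 | 0.99 | 0.12 | 0.54 | out, as it should be |
| 8/8 vs 9/45 | 0.995 | <0.0001 | <0.0001 | out |
| 0/20 vs 12/44 | 0.993 | 0.001 | 0.012 | out |

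In the first four rows the association weakens from top to bottom, yet only the strongest is excluded.

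**Chance of passing p<0.10.** I enumerated all binomial outcomes for 53 patients, counting any outcome with a level of no or only responders as a Wald failure. Entries are Wald / likelihood ratio / Fisher.

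| True ORR in the level | Level of 20, 40% elsewhere | Level of 10, 45% elsewhere |
|---|---|---|
| 20% | 40% / 49% / 40% | 27% / 47% / 38% |
| 10% | 64% / 83% / 76% | 33% / 78% / 67% |
| 5% | 56% / 95% / 92% | 24% / 92% / 84% |
| 2% | 31% / 99% / 97% | 12% / 98% / 94% |
| 0% | 0% / 100% / 100% | 0% / 100% / 100% |

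With no effect (levels of 10 and 43, 40% in both) the pass rates are 0.080 for Wald, 0.108 for the likelihood ratio and 0.073 for Fisher.

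**The case against.** The strongest reply is that the SAP never says the screen is a Wald test. The word appears only in an appendix table shell, and the section that sets the screen also names Fisher's exact test. If Fisher is meant, the failure does not occur. This stands as a limit on attribution. But the shell is the only univariate response output the SAP defines, so the screening test must be stated whichever was intended.

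A reader might infer that strong predictors in general are thrown out. The table above does not support this: 1/20 and 2/20 against the rest both pass. Only categorical covariates with a level of no or only responders are affected, and several listed covariates (age, albumin, sum of target lesion diameters) are not categorical.

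A reader might also infer that the loss grows steadily with the effect. The Wald pass rate first rises (27% to 33%, or 40% to 64%) and then falls to 0%. At 20% against 40%, with levels of 20 and 33, Wald and Fisher pass equally often.

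Nor do the documents show that such levels are likely for CNS metastases, lobular histology, HER-2 or race, since they give no level sizes. A small empty level is not evidence of an effect. Fisher p falls below 0.10 only from 7 patients in the level at 17/53, from 14 at 12/64, and from 9 at 4/20 (the Cohort A1 activity threshold).

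Finally, a level with no responders is not necessarily hidden. Table 11.3.1.2 gives ORR with an exact CI for the pre-specified Cohort A subgroups, and a diverged odds ratio would be visible in Table 11.3.3.1. That softens the consequence for those subgroups but does not repair the selection rule.

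**Conclusion.** The point holds in a limited form. If the 0.10 screen is read from Table 11.3.3.1, a categorical covariate with a level of no or only responders is excluded from the response model however strong the evidence, and weaker covariates are kept. At 17/53 the contrast is Wald p = 0.995 for 0/20 vs 17/33 against 0.008 for 1/20 vs 16/33. For a level with a true ORR of 5%, the chance of passing is 56% with Wald and 95% with the likelihood ratio for a level of 20 (40% elsewhere), and 24% against 92% for a level of 10 (45% elsewhere).

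These sizes rest on assumed level sizes and response rates, and on Wald being the screening test, which the shell implies but the text does not state. The models are exploratory. The primary ORR with its exact CI and the futility rules do not depend on them. The change is still worth making before analysis, because the fault is specific and the correction nearly free.

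**What to change.** In SAP 6.2.2 and Tables 11.3.3.1 and 11.3.3.2:

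- State that the 0.10 screen for response uses the likelihood-ratio p-value, or Fisher's exact p-value for categorical covariates, and change the Wald column to match.
- Name the likelihood-ratio test for stepwise removal. With a Wald removal test at 0.05, a covariate that passed the corrected screen would be dropped again.
- Where a level has no or only responders, report the odds ratio from Firth penalised likelihood with a profile-likelihood 95% CI. Firth is needed only for this reporting; the pass rates above are for the ordinary likelihood-ratio test.

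The cost is SAP wording, a column header and a model option, with no new data. The likelihood-ratio screen is slightly liberal in small samples (0.108 against a nominal 0.10 in the case above). It also admits smaller empty levels than Fisher does: 0/5 vs 17/48 gives 0.043 against 0.163. A sponsor who wants to avoid that can choose Fisher for the categorical covariates.
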